# 9.4.3. Analyses of exploratory immunogenicity endpoints

Additional exploratory immunological assays evaluating S-specific or disease-related antigen specific humoral or cellular immune responses, including but not limited to antibody functionality (Fc $\gamma$  R binding capacity, IgG affinity), isotype titer and isotype avidity, deep immunophenotyping of cellular responses might also be performed. The analyses will be performed separately for study Part A and Part B participants. In addition, pooled analyses where groups common in Part A and Part B are combined as one group respectively will be performed. Appropriate pooled analyses, such as the ANCOVA planned on neutralizing antibody titers will also be performed on the IgG antibody responses.

Analysis of tertiary endpoints detailed in Section 3 will be described in the SAP.

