GMR from baseline (D1) of neutralizing titer against pseudovirus bearing S protein from vaccine encoded SARS-CoV-2 and WT strains at each collection timepoint.	GMR from baseline of neutralizing titer against pseudovirus bearing S protein from vaccine encoded SARS-CoV-2 and WT strains will be tabulated with 95% CI at each post vaccination visit by treatment. The 95% CI will be calculated based on the t-distribution of the log-transformed fold rise value for GMR, then back- transformed to the original scale for presentation. Bar charts (including 95% Cls) of GMR in log2 scale at
	each post vaccination visit by treatment will be provided. At each post vaccination timepoint, the adjusted GMRs from baseline of neutralizing titer, with their 95% CI, will be obtained using an ANCOVA on log10 transformed

Secondary Immunogenicity Endpoints	Statistical Analysis Methods
	titers with treatment group as a fixed factor, and log10 transformed Day 1 baseline value as a covariable. Once Part B data are available, Part A and Part B data will be pooled together for model based analyses. When pooled, the study part will be added as a fixed factor and adjusted GMR will be estimated under Part A condition. Groups common in Part A and Part B will be combined as one group respectively for the pooled analysis. Outputs will be displayed by 3 µg, 10 µg, 30 µg, 100 µg, and pooled placebo.
	In addition, the similar ANCOVA model for GMR from baseline will be performed to further evaluate the linear dose effect, using dose level as a continuous variable.
Vaccine response rate based on neutralizing titers against vaccine encoded SARS-CoV-2 and WT strains at each collection timepoint.	The number and percentage with exact 95% CI of participants with vaccine responses of at least a 2, 4, and 8 fold increases from Day 1 baseline, with their exact 95% CI will be tabulated by treatment and visit.

The following SAS code will be used to calculate GMT/GMR from baseline, where LOGVAL is the log10 transformed GMT/GMR values at each post vaccination point, and Base is log10 transformed pre-dose GMT value. The analyses will be performed on PPS only.

```
Proc sort data = study; by group step; run; /** group will be sorted with order of Placebo, 3, 10, 30, 100***/;
```

```
proc MIXED data=study;
```

```
class group (ref='Placebo') step (ref='1'); /**step='1' indicates Part B, base=log pre-vaccination titer**/;
model LOGVAL = BASE group step/ solution noint;
```

	-	

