estimate 'Placebo'	base X	group 0 0 0 0 1 step 1 0/ cl;
estimate '3'	base X	group 1 0 0 0 0 step 1 0/ cl;
estimate '10'	base X	group 0 1 0 0 0 step 1 0/ cl;
estimate '30'	base X	group 0 0 1 0 0 step 1 0/ cl;
estimate '100'	base X	group 0 0 0 1 0 step 1 0/ cl;
de output actimatac=a	stmenolin	

ods output estimates=estmrnalin;

quit;

```
where X is GMT at pre-dose across groups for Part A.
```

The following SAS code will be used to further evaluate the linear dose effect on GMR from baseline of neutralizing titer against pseudovirus bearing S protein from vaccine encoded SARS-CoV-2 and WT strains, where LOGVAL is the log10 transformed GMR values at each post vaccination point, and Base is log10 transformed pre-dose titer value. The analyses will be performed on PPS only.

```
proc MIXED data=study;
```

class step (ref='1'); /**step='1' indicates Part B, base=log pre-vaccination titer**/;			
model LOGVAL = BASE dose step/ solution;			
estimate	'Placebo'	intercept 1 base X dose 0	step 1 0/ cl;
estimate	'3'	intercept 1 base X dose 3	step 1 0/ cl;;
estimate	'10'	intercept 1 base X dose 10	step 1 0/ CL;
estimate	'30'	intercept 1 base X dose 30	step 1 0/ CL;
estimate	'100'	intercept 1 base X dose 100	step 1 0/ CL;
ods output estimates=estmrnalin;			
quit;			
where X is GMT at pre-dose across groups for Part A.			

Geometric mean ratios (GMRs) will be computed at each sampling timepoint after dosing versus baseline (D1). The GMRs and 95% Cis will be constructed by exponentiating (base 10) the means of within-participant differences between log-transformed titers after each sampling timepoint and log-transformed titers at baseline. GMR will be calculated only for participants with valid baseline immunogenicity results.

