## 4.4.1. Analysis of Serum-Binding Antibody (IgG)

If more than 10% of participants are eliminated from any of the PPS in any treatment group, a sensitivity analysis will be carried out using the Exposed Set.

4.4.1.1. GMCs and GMR from baseline of binding IgG Ab against SARS-CoV-2 Spike WT (D614), SARS-CoV-2 Spike BA.5, SARS-CoV-2 Spike D614G, SARS-CoV-2 Spike (B.1.617.2, AY.4), SARS-CoV-2 Spike (B.1.1.529, BA.1, BA.1.15), SARS-CoV-2 Spike BQ.1, SARS-CoV-2 Spike XBB.1, SARS-CoV-2 Spike BA.2.275, SARS-CoV-2 Spike XBB.1.5, SARS-CoV-2 Spike XBB.1.16 variants at each collection timepoint

The descriptive summary will consist in the number of results available (N), standard deviation, median, interquartile, minimum, and maximum, GMC/GMR, and associated 95% CIs.

Immunogenicity of the study vaccine will be assessed through GMCs with associated CI at each collection time point before the vaccination (Day 1) and after the vaccination (Day 15, Day 31, M6). Likewise GMRs from baseline, percentage above Lower Limit of Quantitation (LLOQ), and corresponding 95% CI will be reported. The corresponding bar charts for GMC and GMR will be provided in log scale (log10 will be used for GMC while log2 will be used for GMR). For these analyses, CI for GMC and GMR will be derived from a student distribution assuming that log-transformed concentration is normally distributed with variance specific to each treatment group.

Distribution of geometric mean concentration fold changes from baseline for at least 2, 4, and 8 folds, with their exact 95% CI will be tabulated, by study group and visit.

The GMC at each post dose time point, the GMR from baseline, and the 95% CIs in all treatment groups will also be analysed using an ANCOVA model on log10 transformed concentrations with treatment group as fixed in the model, and log10 transformed Day 1 baseline value as covariable.

Once Part B data are available, Part A and Part B data will be pooled together for model based analyses. When pooled, the study part will be added as a fixed factor and adjusted GMC or GMR from baseline will be estimated under Part A condition. Groups common in Part A and Part B will be combined as one group respectively for the pooled analysis. Output will be displayed by 3  $\mu$ g, 10  $\mu$ g, 30  $\mu$ g, 100  $\mu$ g, and pooled placebo.

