#### 6.2.3.6. Geometric mean titres (GMTs) and GMCs

Geometric Mean Titre (GMT) or GMC calculations are performed by taking the inverse logarithm of the mean of the log titre or concentration transformations. Non quantifiable antibody titres or concentrations will be converted as described in Section 6.2.3.5 for the purpose of GMT/GMC calculation. The cut-off value is defined by the laboratory before the analysis. If not otherwise specified, the cut-off refers to the LLOQ.

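### The SAS code for the pooled ANCOVA evaluates a log10 baseline covariate at a titer-scale GMT, so the adjusted GMTs, GMRs and their intervals are unusable if it is run as written

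*SAP*

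**What the plan says.** SAP 4.3.2.1 gives two PROC MIXED blocks for the pooled neutralizing-titer analysis: one with treatment group as a factor, one with dose as a continuous variable. Both include baseline (BASE) and study part (STEP).

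- **Scale of the covariate.** Before the first block: "Base is log10 transformed pre-dose GMT value". In the code comments: "base=log pre-vaccination titer". Before the second block: "Base is log10 transformed pre-dose titer value".
- **Scale of the response.** Also log10: "LOGVAL is the log10 transformed GMT/GMR values at each post vaccination point".
- **Evaluation point.** Every ESTIMATE statement sets BASE to X. After each block, X is defined in the same words: "where X is GMT at pre-dose across groups for Part A".
- **Meaning of GMT.** SAP 6.2.3.6 says a GMT is obtained by "taking the inverse logarithm of the mean of the log titre or concentration transformations", which is a value on the titer scale.

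The prose of SAP 4.3.2.1 specifies the model correctly, with log10 response and log10 baseline covariate, and says that pooled estimates refer to Part A. It does not give the baseline value at which the adjusted means are taken. The sentence after each block is the only definition of X.

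**The concern.** The value put in for a covariate must be on the covariate's own scale. Here the covariate runs over log10 titers (a GMT of 100 is 2 on that scale), but the definition tells the programmer to enter 100. The adjusted mean is then read off the regression line at a log10 baseline of 100, a titer of 10^100.

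**Affected:** the level and confidence interval of every adjusted GMT and GMR from the pooled model, for both strains and each post-vaccination timepoint, and the fitted values from the linear-dose block. The code requests only per-group or per-dose estimates, so each of its ESTIMATE results depends on X.

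**Not affected:** between-group ratios of adjusted estimates (X is common and there is no baseline-by-group interaction), the linear-dose slope, the unadjusted GMT and GMR tables, the response rates, and a Part A-only ANCOVA without STEP.

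Timing also matters. The pooled code is used only once Part B data exist. Under SAP 4.8.1 the sponsor's statistical team is by then unblinded to individual participants.

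**Working it through.** **Inputs from the documents**
- Pseudovirus neutralization LLOQ: 10 for both strains; values below the cut-off become cut-off/2 = 5 (SAP 6.2.3.5). The pre-dose GMT therefore cannot be below 5.
- Per-protocol n of 16 per vaccine group and SD 0.45 for the log10 increase from Day 1 (SAP 5).

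**Assumptions (not in the documents)**
- Slope b of post-dose on pre-dose log10 titer: 0.2 to 0.8.
- Baseline GMT: 5, 10 or 100.
- Baseline SD: 0.3 to 0.7 log10.
- Residual SD: 0.45, borrowed from SAP 5.
- Per-protocol placebo: 16 in Part A and 5 in Part B.

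**The plan's own figure.** SAP 5 gives 1.74 for the ratio of upper limit to GMR: 10^(2.131 × 0.45/√16) = 10^0.240 = 1.74. It reproduces. The SAP gives no figure for the pooled ANCOVA.

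**Shift in the point estimate.** Each ESTIMATE returns group effect + Part A effect + b·X. Replacing X = log10 GMT by X = GMT adds
- adjusted log10 GMT: b × (GMT − log10 GMT)
- adjusted log10 GMR: (b − 1) × (GMT − log10 GMT), because the slope of log fold-rise on baseline is b − 1.

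| Baseline GMT | GMT − log10 GMT | GMT shift, b = 0.2 | GMT shift, b = 0.8 |
|---|---|---|---|
| 5 (floor) | 5 − 0.699 = 4.30 | 0.86 (7-fold) | 3.44 (about 2,750-fold) |
| 10 | 10 − 1 = 9.0 | 1.8 | 7.2 |
| 100 | 100 − 2 = 98.0 | 19.6 | 78.4 |

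Shifts are in log10 units. The GMR shift covers the same range with negative sign: at GMT 10 it is −7.2 at b = 0.2 and −1.8 at b = 0.8. The two errors cannot vanish together, since one needs b = 0 and the other b = 1.

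**Confidence interval, 10 µg group.** Per-protocol n is 4 × 16 in Part A (placebo, 10, 30 and 100 µg) plus 5 + 16 + 16 in Part B (placebo, 3 and 10 µg), which is 101. The model has 7 free parameters, leaving 94 df and t = 1.986.
- At X = log10 GMT the half-width is 0.21 log10 (1.6-fold).
- Away from the mean, the slope's uncertainty adds about t × SE(b) × (GMT − log10 GMT), with SE(b) ≈ 0.45/(baseline SD × √95). That is 0.154 at SD 0.3 and 0.066 at SD 0.7.
- GMT 10: 1.986 × 0.066 × 9 ≈ 1.2 to 1.986 × 0.154 × 9 ≈ 2.8 log10.
- GMT 100: about 13 to 30 log10 by the same formula with 98 in place of 9.

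Inverting the full design matrix gives the same values.

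**Simulated check.** One dataset with a baseline GMT of 121.18 (log10 = 2.08), 10 µg group:

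| | X = log10 GMT | X = GMT |
|---|---|---|
| Adjusted log10 GMT (95% CI) | 2.43 (2.26 to 2.60) | 65.00 (43.63 to 86.38) |
| Adjusted log10 GMR (95% CI) | 0.34 (0.17 to 0.51) | −56.18 (−77.55 to −34.80) |
| 10 µg minus placebo, log10 | 0.180 | 0.180 |

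The fitted slope is (65.00 − 2.43)/(121.18 − 2.08) = 0.525, and 0.34 + (0.525 − 1) × 119.10 = −56.2, as the formulas predict. In the linear-dose block the fitted log10 GMR at 10 µg goes from 0.31 to −56.31, while the dose slope is unchanged.

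**The case against.** The strongest reply is that X is only a placeholder for a value of BASE, that BASE is labelled as log10 beside the code, and that this section uses GMT loosely: it calls individual participants' log values GMT/GMR values. On that reading the authors meant log10 GMT, and a competent programmer would enter it. This is plausible as to intent. But the same section writes the log10 qualifier where it means the log scale, and both definitions of X omit it. A literal reading gives the wrong number.

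Second, an error of 20 to 78 powers of ten would be caught against the unadjusted tables. That is probably right at any baseline well above the assay floor. It is less certain near the floor with a shallow slope, where the GMT is off by about 7-fold, although nothing in the documents says the baseline lies there.

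Third, a correction after unblinding leaves no room for an outcome-driven choice, because it is unique and uses only pre-dose data. This largely stands. The remaining cost is an avoidable change to prespecified code made by an unblinded team.

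Fourth, the study is descriptive, the endpoints are secondary, and contrasts between groups are intact. All true. This limits the reach of the error but does not make the stated rule correct.

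Finally, the IgG analysis in SAP 4.4.1.1 has no code and no X, so no error is shown there. That is accepted; the IgG point is conditional on reuse.

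**Conclusion.** The concern holds. As written, the only definition of the evaluation point is on the wrong scale in both code blocks, and literal use makes the pooled adjusted GMTs, GMRs and intervals unusable. The direction and the closed-form shift follow from the SAP alone, for any slope between 0 and 1. The sizes rest on the assumed slope, baseline GMT and SDs. The floor of 5 does not, and even there the GMT error is about 7-fold to 2,750-fold for b = 0.2 to 0.8.

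It should be fixed before the pooled analysis is programmed. It is a definite error in prespecified code for secondary endpoints, with limited reach and a good chance of detection.

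The IgG analysis could inherit it: the SAP says that "adjusted GMC or GMR from baseline will be estimated under Part A condition", and Protocol 9.4.3 says that pooled analyses "such as the ANCOVA planned on neutralizing antibody titers will also be performed on the IgG antibody responses". If the code were reused, the smallest possible GMC is 60 AU/mL (half the XBB.1 LLOQ of 120), and the GMC shift at b = 0.2 would be at least 0.2 × (60 − 1.78) = 11.6 log10.

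**What to change.** In SAP 4.3.2.1, replace the sentence that defines X after each of the two code blocks with: *X is the mean of the log10 pre-dose titers across groups in Part A, that is, log10 of the pre-dose GMT.* If the code is reused for the IgG ANCOVA in SAP 4.4.1.1, apply the same definition there with log10 concentrations.

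The cost is two sentences. The model, the data and the list of outputs stay as they are, nothing is traded away, and no change to the continuous-dose model is requested.

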## 4.3.2.2. Additional considerations

NA.

# 4.4. Tertiary Endpoint(s) Analyses

The analysis will be based on the PPS.

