# 8.2. Immunogenicity assessments

Blood samples will be taken to assess both the humoral and cellular immune responses induced by the vaccine candidate on Day 1, Day 15, Day 31, and Month 6.

In addition, biological samples will be used for research planned in the protocol and for purposes related to the improvement, development and quality assurance of the laboratory tests described in this protocol.

Findings in this or future studies may make it desirable to use samples acquired in this study for research not planned in this protocol. In this case, all participants in countries where this is allowed will be asked to give consent to allow GSK or a contracted partner, to use the samples for further research. The further research will be subject to prior IEC/IRB approval, if required by local legislation.

Information on further research and its rationale can be obtained from GSK.

Sample testing will be done in accordance with the recorded consent of the individual participant.

By default, collected samples will be stored for a maximum of 20 years. This storage period begins when the last participant performs the last study visit. This timeline can be adapted based on local laws, regulations or guidelines requiring different timeframes or procedures. In all cases, the storage period should be aligned with participant's consent. These additional requirements must be formally communicated to, discussed, and agreed with GSK.

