# 9.3. Analysis sets

#### Table 17Analysis sets

Analysis set	Description
Screened	All participants who were screened for eligibility.
Enrolled	Participants who completed the informed consent process, meet screening/eligibility criteria and undergone an invasive procedure. Note: screening failures (who never passed screening even if re-screened) and participants screened but never enrolled into the study (Met eligibility but not needed) are excluded from the Enrolled analysis set as they did not enter the study.
Exposed	All participants who received the dose of the study intervention. Analysis per group using the enrolled set based on the administered intervention.
Per Protocol	All eligible participants who received dose of study intervention as per protocol, without intercurrent conditions that may interfere with immunogenicity and without prohibited concomitant medication/vaccination, and who have values for pre-dose and post-dose neutralizing antibody titer against pseudovirus bearing S protein data for the relevant timepoint, and without major protocol deviations. The PPS for immunogenicity will be defined by time point.
Solicited Safety	All participants who received the dose of the study intervention (Exposed Set) who have reported the presence or absence of any solicited AE at least once.

AE: Adverse event; D: Day; S: Spike; PPS: Per Protocol Set

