### 9.3.1. Criteria for elimination from analysis

If a participant meets one of the criteria mentioned below, they may be eliminated from per protocol analysis.

- Receive any of the medications/products/vaccines listed in Section 5.2.2.
- Incur an intercurrent medical condition that could alter their immune response (i.e., varicella, HIV, lymphoma) or are confirmed to have an alteration of their initial immune status.
- Major protocol deviation(s) linked to the eligibility criteria (Section 5.1 and Section 5.2).
- Study intervention not administered as specified by the protocol.
- Failure to comply with the post-dose immunogenicity blood sampling schedule at a given timepoint (Section 1.3).
- Other major protocol deviation during vaccination phase that led to exclusion.

The SAP will provide a complete list of criteria for elimination from PP analyses.

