Secondary	One dose of the investigational mRNA-CR vaccine.	Healthy adults, 18 to 49 years of age, who were primed and received booster dose(s) of an authorized or licensed mRNA COVID -19 vaccine with the last booster dose administered at least 6 months or more prior to	the 15-day follow-up period after study vaccine administration (day of study vaccine administration and 14 subsequent days); • MAAEs; SAEs; AESIs up to D31. MAAEs; SAEs; AESIs from Day 1 up to study conclusion (M6).	•	Study vaccination not administered as per protocol Any intercurrent conditions or any concomitant medication/vaccination that may confound the safety investigational product causality assessment prior to M6	The data collected from all participants receiving one dose of investigational vaccine will be used regardless of whether the intercurrent event occurs (Treatment policy) Rationale: treatment policy strategy is used as all data will contribute to evaluate the safety parameters	Proportion of participants in each treatment group for each endpoint

Estimand			Att	ribut	es		
	Treatment	Population	Endpoint (Variable)	ble) Intercurrent events (ICEs)		- Summent	
					Description	Handling strategy	Summary measure
		inclusive at the time of the vaccination.					
Secondary	One dose of the investigational mRNA-CR vaccine.	Healthy adults, 18 to 49 years of age, who were primed and received booster dose(s) of an authorized or licensed mRNA COVID -19 vaccine with the last booster dose administered at least 6 months or more prior to screening, inclusive at the time of the vaccination.	Neutralizing titer against pseudovirus bearing S protein from vaccine encoded SARS-CoV-2 and WT strains at each collection timepoint (D1, D15, D31, M6).	•	Study vaccination not administered as per protocol A condition that has the capability of altering the immune response (e.g., HIV, lymphoma, COVID) to the study intervention or is confirmed to have an alteration of the participant's initial immune status Major protocol deviations including out of visit window blood samples.	The Hypothetical strategy will be used. The data after the ICEs will be ignored. Rationale: To estimate the treatment effect on participants who are dosed and have no major protocol deviations.	Geometric Mean Titer for each treatment group

Estimand		Attributes							
	Treatment	Population	Endpoint (Variable)		Intercurrent ev	vents (ICEs)	Summani		
					Description	Handling strategy	Summary measure		

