# 3. ANALYSIS SETS

## 3.1. Definition

#### Table 5Analysis sets

Analysis set	Description	Analyses Evaluated
Screened	All participants who were screened for eligibility.	Study Population
Enrolled	Participants who completed the informed consent process,	Study Population
	meet screening/eligibility criteria and undergone an invasive	
	procedure.	
	Note: screening failures (who never passed screening even if	
	re-screened) and participants screened but never enrolled	
	into the study (Met eligibility but not needed) are excluded	
	from the Enrolled analysis set as they did not enter the study.	
Exposed	All participants who received the dose of the study	Safety excluding solicited AE
	intervention. Analysis per group using the enrolled set based	
	on the administered intervention.	
Per Protocol	All eligible participants who received dose of study	Immunogenicity
	intervention as per protocol, without intercurrent conditions	
	that may interfere with immunogenicity and without prohibited	
	concomitant medication/vaccination, and who have values for	
	pre-dose and post-dose neutralizing titer against pseudovirus	
	bearing BA. 5 S protein data for the relevant timepoint, and	
	without major protocol deviations.	
	The PPS for immunogenicity will be defined by time point.	
Solicited	All participants who received the dose of the study	Safety
Safety	intervention (Exposed Set) who have reported the presence	
	or absence of any solicited AE at least once.	

AE: Adverse event; D: Day; S: Spike; PPS: Per Protocol Set

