## 4.4.3. Incidence of confirmed symptomatic and asymptomatic SARS-CoV-2 infection

The percentage of participants of laboratory-confirmed SARS-CoV-2 by N protein seroconversion at either (D15, D31, and M6) or RT-PCR at either (D8, D15) will be summarized by treatment.

Percentage of laboratory-confirmed (RT-PCR) SARS-CoV-2 infection reported as AESI post-vaccination will be summarized by treatment.

Percentage of laboratory-confirmed (RT-PCR) SARS-CoV-2 infection reported as AESI or SARS-CoV-2 detected by N-protein and R-PCR post-vaccination will be summarized by treatment.

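### SAP 4.4 puts the SARS-CoV-2 infection percentages of 4.4.3 on the Per Protocol Set, a titer-based set defined by time point that does not fit them and that infection itself may remove participants from

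*SAP*

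**What the plan says.** SAP 4.4 gives one rule for every tertiary endpoint: "The analysis will be based on the PPS". Section 4.4.3 lies under that rule and names no other set. Its first summary is "The percentage of participants of laboratory-confirmed SARS-CoV-2 by N protein seroconversion at either (D15, D31, and M6) or RT-PCR at either (D8, D15"). Its second reads "Percentage of laboratory-confirmed (RT-PCR) SARS-CoV-2 infection reported as AESI post-vaccination will be summarized by treatment". The third combines AESI reports with infections detected by N-protein serology and RT-PCR.

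SAP Table 5 assigns the PPS to immunogenicity. It requires pre-dose and post-dose BA.5 neutralizing titers, and "The PPS for immunogenicity will be defined by time point". Protocol Table 17 limits the set to participants "without intercurrent conditions that may interfere with immunogenicity and without prohibited concomitant medication/vaccination", and SAP Table 5 does the same. Protocol 8.2 has blood drawn for the immune responses "induced by the vaccine candidate on Day 1, Day 15, Day 31, and Month 6".

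On whether infection is such a condition, the documents differ. SAP Table 2 lists, as an intercurrent event for the titer estimands, "A condition that has the capability of altering the immune response (e.g., HIV, lymphoma, COVID) to the study intervention". Protocol 9.3.1 gives varicella, HIV and lymphoma, does not name COVID, and says of participants who meet a criterion that "they may be eliminated from per protocol analysis".

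**The concern.** There are two problems, and the first does not depend on the second.

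- **Fit.** A set defined by titer availability at Day 15, Day 31 and Month 6 gives no rule for a percentage that also uses RT-PCR at Day 8 and accumulates to Month 6. Two programmers following the SAP could obtain different denominators from the same data.
- **Selection on the outcome.** Leaving out infected participants can be sensible when the question is the titer produced by the vaccine. It is not sensible when the question is how many were infected, because the event being counted can then remove the participant from the count.

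At stake is the correct reporting of a tertiary, descriptive endpoint. The primary and secondary analyses and the sample size are untouched. A further consequence is that the AESI-based percentage in 4.4.3 (PPS) and the AESI tables (Exposed Set) could show different figures for the same events in one report.

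**Working it through.** **1. Which set applies to 4.4.3.** SAP 4.1 makes the Exposed Set the default for safety endpoints unless another set is specified. Infection incidence is listed as tertiary in SAP Table 1, and 4.4 does specify a set. SAP 4.9 changes only the use of RT-PCR at screening and Day 1. Protocol 9.4.3 leaves the tertiary analyses to the SAP. The rule in 4.4 therefore stands.

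**2. Tests in 4.4.3 against available PPS time points.**

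| Test visit | RT-PCR | N serology | Post-dose PPS |
|---|---|---|---|
| Day 8 | yes | no | none |
| Day 15 | yes | yes | Day 15 |
| Day 31 | no | yes | Day 31 |
| Month 6 | no | yes | Month 6 |

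Day 8 has no PPS, and the composite spans all four rows.

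**3. Fallback.** The Exposed Set sensitivity analysis, triggered when more than 10% are eliminated, is written in SAP 4.3.2.1 (neutralizing titers) and 4.4.1 (binding IgG). It is not in 4.4.3.

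**4. Effect if infection leads to removal.** The plan states no infection figure to reproduce. Let p be the true incidence and q the share of infected participants removed, for one PPS at one time point, with no removals for other reasons. Among those left,

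reported = p(1 − q) / (1 − pq).

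For example, p = 10% and q = 50% gives 0.05 / 0.95 = 5.3%. Both p and q are assumptions:

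| p | q = 0 | 25% | 50% | 75% | 100% |
|---|---|---|---|---|---|
| 5% | 5.0 | 3.8 | 2.6 | 1.3 | 0 |
| 10% | 10.0 | 7.7 | 5.3 | 2.7 | 0 |
| 20% | 20.0 | 15.8 | 11.1 | 5.9 | 0 |

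(reported percentage)

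**5. The same in counts.** Assume 4 infections, 2 of them removed, with exact (Clopper-Pearson) 95% intervals.

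- Pooled placebo, n = 3 × 6 + 6 = 24: 4/24 = 16.7% (4.7 to 37.4) becomes 2/22 = 9.1% (1.1 to 29.2).
- One vaccine group, n = 18: 4/18 = 22.2% (6.4 to 47.6) becomes 2/16 = 12.5% (1.6 to 38.3).

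The point estimate moves noticeably, but the intervals overlap widely.

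**6. The Exposed Set alone does not settle the denominator.** Suppose 2 of 18 have no test and count as non-cases. This borrows the plan's 16 evaluable for titers and assumes equal incidence in tested and untested. Incidence is then multiplied by 16/18 = 0.889: 20% becomes 17.8% and 10% becomes 8.9%. In addition, the Schedule of Activities stops scheduled RT-PCR at Day 15. After that visit, asymptomatic infection in someone already N-positive at Day 1 has no scheduled test that would show it as a seroconversion.

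**The case against.** A reader might infer that the infection percentages will be biased toward zero. The documents do not support that. Elimination under Protocol 9.3.1 is discretionary and its examples omit COVID. The mention of COVID in SAP Table 2 concerns the secondary titer estimands and says that data after the event are ignored; it is not a rule for removing participants, and Table 2 has no tertiary estimand. Neither document says whether asymptomatic seroconversion counts. A participant infected after Day 31 stays in the Day 15 and Day 31 sets. Nor is the direction guaranteed once other removals are allowed: if two non-cases are dropped instead, 4/18 = 22.2% becomes 4/16 = 25.0%. All of this stands, so the bias is conditional. The mismatch of set and endpoint is not.

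A reader might also infer that infections would disappear from the report. They would not. AESIs, including virologically confirmed COVID-19, are tabulated on the Exposed Set to Day 31 and to Month 6 (SAP 4.2.1.1, 4.2.1.3, 4.3.1.1). Asymptomatic infections documented as AEs under Protocol 8.4.4.2.2 enter the unsolicited-AE tables to Day 30. SAP 4.6.1 lists every infection category and all COVID-19 test results on the Exposed Set, and SAP 6.1.1 counts PPS exclusions. With groups this small, a careful reader could count cases from the listings. That narrows the point considerably. But a listing is not a percentage, and neither N-seroconversion nor the combined endpoint has a planned Exposed Set percentage. The gap matters most for asymptomatic infection first shown by Month 6 serology, because general AE collection ends at Visit 4 (Protocol 8.4.1).

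**Conclusion.** The concern holds as a mismatch between analysis set and endpoint, with a conditional risk of understatement. That 4.4 governs 4.4.3, that Day 8 has no PPS, and that no single PPS fits the composite all follow from the text without assumptions. Understatement requires that infected participants be removed more often than others. If they are, and nobody is removed for another reason, the reported percentage is below the true one for any q above 0 and is 0 when all are removed. Its size in this trial cannot be stated.

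The effect is confined to the N-seroconversion and combined percentages, and to possible disagreement between the 4.4.3 AESI percentage and the AESI tables. Because the endpoint is tertiary and descriptive and no hypothesis is tested, this should be corrected for accurate reporting; no trial conclusion depends on it.

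**What to change.** In SAP 4.4.3, state that the section overrides 4.4 and uses the Exposed Set, with these denominators:

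- **AESI-based percentage:** all exposed participants, so that it matches the AESI tables.
- **N-seroconversion:** by time point, among exposed participants who are N-negative at Day 1 and have an N result at that time point.
- **RT-PCR:** by visit, among exposed participants with a result at that visit.
- **Combined percentages:** all exposed participants, with the number lacking complete testing shown for each treatment group. Describe the result as detected infections, a minimum. Do not present it as incidence to Month 6 among those with at least one test: someone with only a Day 8 RT-PCR would then count as uninfected to Month 6.

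The cost is a few sentences and slightly more tabulation. RT-PCR and N serology are already collected, so no new data are needed.
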